**Blind vs. Ultrasound-guided Corticosteroid Injections for de Quervain's disease:
A Prospective Study**

NCT02038634

February 6, 2018

Background:

De Quervain's disease is the stenosing tenosynovitis and tendinitis of the abductor pollicis longus (APL) and extensor pollicis brevis (EPB) tendons in the first dorsal compartment of the wrist. While the prevalence of de Quervain's is not yet well-established, previous studies have shown that women can be affected by the disease up to six times more frequently than men.^{5,6} Conservative treatments include splinting and corticosteroid injections, but surgery is an option when such therapy fails. One study⁶ compared the improvement rates of patients treated with splinting alone, injection and splinting, and injection alone, and found the rate of improvement to be 19%, 57%, 67%, respectively. This confirmed the good results reported in previous studies^{1,3} and recommends corticosteroid injection to clinicians as a reliable treatment for de Quervain's disease.

A seminal study performed by Zyngas *et al.*⁷ correlated the accuracy of corticosteroid injection with pain relief by including X-ray dye in the injection. The results of the study suggested a strong correlation between accurate injection of the first dorsal compartment and pain relief. Since then, the use of ultrasonography (US) to guide steroid injection has been suggested as a possible clinical practice, but little research has been done on the technique. A 2009 study⁴ reported a 93.75% rate of significant pain relief after the use of US-guided injections, but there was no control group with which to compare results. The current standard practice for steroid injection in de Quervain's patients is a blind injection without imaging guidance. To our knowledge, no study has compared the clinical outcomes of blind injections to US-guided injections. We hypothesize that the US-guided injections will result in greater pain relief for patients than blind attempts

Study Design:

This is intended to be a prospective study. Patients will contact the PI for a standard clinical evaluation, which includes palpation of the first extensor compartment and application of the Finkelstein test.² Those diagnosed with de Quervain's disease and who fit all inclusion criteria will receive a detailed verbal description of the study from one of the doctors, who will then attain written, informed consent from willing participants. The PI will then administer either a blind or US-guided injection. The patient will return for follow-up appointments at 6-8 weeks and 12-16 weeks and will undergo another physical exam to determine pain relief. A phone call follow-up will also be placed one year after the injection in order to determine long-term effectiveness. Once 20 study subjects in each group (40 total) have been enrolled and completed treatment, the data will undergo statistical analysis.

This study poses minimal or no physical risk to study subjects, as the US-guided injection should show better accuracy and pain relief for patients than the current standard treatment (blind injection).

All Injections will consist of 6 mg betamethasone and 4 cc 1% lidocaine without epinephrine, which is standard of care treatment.

In summary, we aim to perform a prospective study to evaluate the effectiveness of blind corticosteroid injections to US-guided injections for the treatment of de Quervain's disease. The results of the study will be used to validate current injection protocols or support the incorporation of ultrasonography to treat the disease.

Risk to Subjects:

A minimal physical risk is temporary inflammation around the wrist which accompanies any steroid injection. There is no risk involved with the addition of ultrasound. There is a slight risk of loss of confidentiality.

Data Analysis:

The mean DASH scores from the control group (blind injection) and the treatment group (US-guided injection) will be compared with a t-test to discern any significant statistical difference.

Plan for evaluating problems and adverse events (AEs):

The PI will address any unforeseen problems or events related to the study and the study coordinator will report promptly to the IRB.

References:

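### The protocol gives no rule for assigning patients to blind or ultrasound-guided injection, so a DASH difference could reflect who received which technique

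*Combined protocol and SAP*

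**What the plan says.** The Study Design section introduces the trial with "This is intended to be a prospective study". It describes evaluation ("Patients will contact the PI for a standard clinical evaluation") and consent, which one of the doctors obtains. The next step is "The PI will then administer either a blind or US-guided injection". Group size is fixed by a count: "Once 20 study subjects in each group (40 total) have been enrolled and completed treatment", the data are analysed.

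No part of the document mentions randomisation, a sequence, concealment, alternation, or choice by patient or physician. Data Analysis labels the arms control and treatment and compares their mean DASH scores with a t-test. It names no baseline DASH value and no covariate.

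The expected direction is on record. Background states "We hypothesize that the US-guided injections will result in greater pain relief for patients than blind attempts", and Study Design repeats the expectation when it argues that the risk is minimal. Study Design also says what the results are for: to validate present injection practice or to support adding ultrasound.

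**The concern.** The intended conclusion is causal: it is about the technique, not about the patients who happened to receive it. A comparison group supports such a conclusion only if technique does not follow severity or prognosis. Background criticises an earlier ultrasound series because "there was no control group with which to compare results". A control group formed by an unstated rule only partly repairs that weakness.

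As written, the plan allows the technique to be chosen with knowledge of the patient. The injector is the PI, whom patients contact for evaluation, and the study team expects ultrasound to do better. Nothing in the analysis would remove a resulting difference between the groups. Its direction is unknown: if harder cases are sent to ultrasound, the bias works against the stated hypothesis.

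**Working it through.** **Reading check.** Each place that could hold an allocation rule was read for one.

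| Place | What it settles | What it leaves open |
|---|---|---|
| Study Design, opening | Prospective data collection | Whether randomised |
| Study Design, injection sentence | Who injects | Who or what picks the technique, and when |
| Study Design, enrolment target | 20 per group, 40 in total | How the two groups are filled |
| Data Analysis | Names of the arms; t-test on mean DASH | Any adjustment for baseline or severity |

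No redaction is visible in these sections. Consent pages were not available for this review. They might mention chance, but the sequence, its holder and the time of reveal belong in the protocol.

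**Illustration of size.** There is no figure in the plan to reproduce: it gives no alpha, DASH SD, baseline value or correlation. From the document: n = 20 per group. Assumed: two-sided alpha 0.05, no true effect, unit-SD normal scores, and a correlation ρ of 0.3, 0.5 or 0.7 between baseline and follow-up DASH.

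*Step 1: a given baseline imbalance.* If the groups differ by b SD at baseline, the expected follow-up difference is bρ SD. The t statistic has n + n − 2 = 38 degrees of freedom and noncentrality bρ√(n/2) = bρ√10. For b = 0.5:

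| ρ | Noncentrality | Chance of a significant result |
|---|---|---|
| 0.3 | 0.5 × 0.3 × 3.162 = 0.474 | 7.5% |
| 0.5 | 0.5 × 0.5 × 3.162 = 0.791 | 12.0% |
| 0.7 | 0.5 × 0.7 × 3.162 = 1.107 | 19.0% |

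*Step 2: how many patients that takes.* Suppose m of the 40 are steered: the worse half of them at baseline goes to one arm, the better half to the other, and the remaining patients are allocated by chance to give exactly 20 per arm. In a large normal sample the two halves differ by 2√(2/π) = 1.596 SD, so the imbalance is roughly (m/2)/20 × 1.596. For m = 20 this is 0.5 × 1.596 = 0.80 SD. The simulated value is slightly lower because the steered set is small. Simulation with 40,000 runs per cell:

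| Steered, of 40 | Mean imbalance (SD) | False positives, ρ = 0.3 / 0.5 / 0.7 |
|---|---|---|
| 0 | 0 | 5.0 / 5.0 / 5.0% |
| 6 | 0.21 | 5.2 / 5.8 / 6.8% |
| 12 | 0.45 | 6.9 / 10.4 / 15.9% |
| 20 | 0.77 | 10.7 / 22.4 / 40.0% |

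Independent re-runs agree within about 0.8 percentage points. ANCOVA on baseline DASH holds the rate at 4.9–5.2% in these cells, but only because this model routes all steering through baseline DASH. Selection on anything else would escape it.

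*Step 3: would more patients help?* No. A selection-induced difference of 0.3 SD in follow-up DASH itself is significant about 15% of the time with 20 per group and about 56% of the time with 100 per group.

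**Check on the remedy.** In a known fixed block of 4, the last assignment is always certain and the third is certain with probability 1/3. Ten blocks give 10 × (1 + 1/3) = 13.3 of 40 assignments known in advance. With blocks of 4 and 6 in an undisclosed order, simulation gives about 2.4 of 40, or about 3.8 if the number of blocks of each size is also known.

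**The case against.** The strongest reply is that the document is silent, and silence is not a choice. Random assignment may have been intended or used, and if so the planned t-test is valid. Evaluating patients before injection and holding a directional hypothesis are both normal in randomised trials, and neither shows selective assignment. It is also an inference that the PI personally evaluates each patient.

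The numbers can be pressed too. Every input except the group size is assumed. The simulation ranks steered patients perfectly on baseline DASH, although the evaluation described names only palpation and the Finkelstein test. Imperfect ranking would produce less imbalance on that score. Even with perfect ranking, steering 6 of 40 barely moves the error rate, and the 40% figure needs half the trial steered and a correlation of 0.7.

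All of this stands as a limit on what can be claimed. The point cannot be put as evidence of bias, and its seriousness cannot rest on the error rates. The reply does not supply the missing rule. Study Design is where that rule belongs, and following it to the letter would permit either a randomised trial or a comparison of selected patients. Two practical points about the remedy also stand: it must cover a trial already randomised by another sound method, and a list of exactly 40 leaves no assignment for a replacement.

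**Conclusion.** The point holds and must be fixed. The protocol contains no allocation rule, and its only analysis gives no protection if technique followed the patient. Until the rule is stated, a DASH difference cannot be read as an effect of ultrasound guidance.

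The conclusion rests on the text alone. The amount of bias, and whether there is any, cannot be determined from the documents. The illustrative false-positive rates run from 5.2–6.8% (light steering) to 10.7–40.0% (half the patients steered), and they depend on the assumed correlations and on the steering model. With no steering the rate is 5.0%.

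**What to change.** First, state how technique is assigned, by whom, and when it is revealed relative to consent. If a sound random method is already in use, describing it and calling the study randomised closes the point.

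If assignment is not yet random, replace the injection sentence with wording such as:

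> After consent, patients are allocated 1:1 from a computer-generated random list in randomly varying blocks whose sizes are withheld from the PI. Just before injection the study coordinator opens the next sealed, opaque, sequentially numbered envelope, and the PI gives the assigned technique.

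Keep the target of 20 per group. Extend the list beyond 40, because the target counts patients who have completed treatment, and keep the block composition out of the protocol. Another concealed random method would serve equally well.

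Optional, for precision only: collect DASH before allocation and compare follow-up DASH by ANCOVA on arm and baseline, at one contact named in advance (for example the 6–8 week visit). At 20 per group, the difference detectable with 80% power falls from 0.91 SD by t-test to 0.88, 0.80 or 0.66 SD at correlations of 0.3, 0.5 and 0.7.

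If patients have already been treated without random allocation, say how technique was chosen, adjust for baseline DASH or severity where recorded, and limit the conclusion to association. Adjustment does not replace randomisation.

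The cost is a short amendment, a set of envelopes, a small task for the coordinator, consent wording on chance allocation, and loss of operator choice of technique. The optional ANCOVA adds one questionnaire.

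### The 20 per group are counted as completers, which allows selection after entry in either arm; count and analyse all patients assigned instead

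*Combined protocol and SAP*

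**What the plan says.** All the relevant text is in the combined protocol and SAP.

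- **Target (Study Design).** "Once 20 study subjects in each group (40 total) have been enrolled and completed treatment, the data will undergo statistical analysis". Completion of treatment is not defined.
- **Diagnosis at entry (Study Design).** This rests on a standard clinical evaluation, "which includes palpation of the first extensor compartment and application of the Finkelstein test". Patients must also meet inclusion criteria, which are not listed. No ultrasound is described at this stage.
- **Order of events (Study Design).** Consent is taken by one of the doctors, "who will then attain written, informed consent from willing participants". The injection follows: "The PI will then administer either a blind or US-guided injection". No method of assigning patients is given.
- **Imaging in the blind arm (Background).** "The current standard practice for steroid injection in de Quervain's patients is a blind injection without imaging guidance".
- **Follow-up (Study Design).** "The patient will return for follow-up appointments at 6-8 weeks and 12-16 weeks", with a telephone call at one year.
- **Analysis (Data Analysis).** Mean DASH scores in the two groups "will be compared with a t-test to discern any significant statistical difference". No analysis population, replacement rule or missing-data method is stated.

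**The concern.** The target sentence sets a time for analysis, but it also settles who makes up the 20. A patient must be enrolled and must have completed. Someone who is enrolled and does not complete leaves a place open, and recruitment to that group may continue until it is filled. Membership of each group then depends partly on what happens after entry. Random assignment, if it were added, would not undo that.

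There are two possible routes.

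- **After a scan.** As described, only the guided arm yields an image after the clinical diagnosis. If a scan raised doubt about the diagnosis and no injection followed, that patient would not be one of the 20. A similar patient in the blind arm would be injected and counted. The possibility of a wrong clinical diagnosis is not far-fetched: the title of reference 2, cited for the Finkelstein test, itself concerns false positives.
- **After a poor result.** If completion includes the return visits, patients who stay away because the injection failed also drop out of the count, in whichever arm they occur.

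At stake is whether the two groups of 20 still represent the same eligible patients. In a study of 40, a few uncounted patients are enough to leave the comparison open to challenge.

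**Working it through.** **1. The plan's own figure.** 20 + 20 = 40 agrees. The size itself cannot be reproduced, because no alpha, power, effect size, SD or dropout rate is given. For scale only: at an assumed two-sided 0.05, 20 per group detects a standardised difference of about 0.91 with 80% power (t-based; 0.89 by the normal approximation).

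**2. Does the rule exclude non-completers on each reading of completion?**

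| Reading | Who falls outside the 20 | Arms affected |
|---|---|---|
| Injection given | Enrolled patients not injected, including any scanned and then not injected | Either; a scan-related reason can arise only in the guided arm |
| Return visits made | The above, plus patients who do not return | Either |

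On both readings an enrolled non-completer is not counted. The readings differ in how many patients this could be.

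**3. Shift in one arm's mean.** Let the 20 counted patients have mean m, and let k uncounted patients score D points worse. The mean of everyone who entered is (20m + k(m + D))/(20 + k) = m + kD/(20 + k). The counted mean is therefore flattered by k/(20 + k) × D. The documents give neither k nor D; both are assumed, with D from 10 to 20 DASH points.

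| k | k/(20 + k) | D = 10 | D = 20 |
|---|---|---|---|
| 1 | 1/21 | 0.48 | 0.95 |
| 3 | 3/23 | 1.30 | 2.61 |
| 4 | 4/24 | 1.67 | 3.33 |

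**4. Net direction.** The bias in the comparison is the ultrasound shift minus the blind shift. With D = 10:

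- k = 3 in ultrasound and 1 in blind: 1.30 − 0.48 = about 0.8 points in favour of ultrasound.
- k = 1 in ultrasound and 3 in blind: 0.48 − 1.30 = about 0.8 points in favour of blind.
- Equal k and D in both arms: zero.

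Nothing in the documents says which case applies.

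**5. False positives if only the ultrasound arm were affected.** This is an extreme one-arm case with no true effect, 20 per group, a two-sided t-test at an assumed 0.05, and 100,000 simulated trials per scenario. A share q of blind patients score g SD worse; all such patients are absent from the ultrasound group. The bias is q × g SD. Both q and g are assumed.

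| q | g | Bias (SD) | Two-sided rejection | Rejection favouring ultrasound |
|---|---|---|---|---|
| 5% | 0.5 | 0.025 | 5.0% | 3.0% |
| 10% | 1.0 | 0.10 | 5.9% | 4.7% |
| 20% | 1.5 | 0.30 | 13.2% | 12.9% |

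The nominal rates are 5% and 2.5%. The mid-range effect is modest; the large figures need the extreme inputs.

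**The case against.** The strongest case against is that the quoted sentence mainly says when analysis starts. The only treatment described is an injection given after consent, so completing it may mean no more than being injected. Ultrasound appears in the plan only as a means of guiding the needle, never as a check on diagnosis or eligibility. No step leaves a scanned patient uninjected, and no sentence says that anyone is replaced.

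Much of this stands. A reader might infer that doubtful cases are dropped and replaced in the ultrasound group only, so that the bias favours ultrasound. The documents do not support that, for three reasons. Dropping a patient after a scan is an inference with no such step in the text. The completer rule applies to both arms. And if blind injections fail more often, as the Background hypothesises, losing patients who stay away after failure would flatter the blind arm. That the blind arm receives no scan is itself a reading of how blind injection is described, not an explicit ban.

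It is also true that the missing allocation method is a larger and separate problem, and that relabelling the denominator does nothing by itself for patients without a score, since a t-test omits them.

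What does not stand is that the rule is therefore harmless. Even on the narrow reading, an enrolled patient who is not injected is outside the 20, and nothing says how that patient is analysed.

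**Conclusion.** The point holds as a weakness in a stated rule: the groups are defined by completion, and nothing keeps an enrolled non-completer in the comparison. Selection after entry is permitted in either arm. That it happens, that it is confined to the ultrasound arm, or that it favours ultrasound is not shown.

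The net direction and size are unknown. The illustration of about 0.5 to 3.3 DASH points is the shift in one arm's mean. It rests on assumed values (1 to 4 uncounted patients, each 10 to 20 points worse), and the documents give no DASH SD to judge it against. The change is worth making because it is cheap and removes a route to bias that randomisation alone would leave open.

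**What to change.** Replace the target sentence in Study Design, and add to Data Analysis, so that the plan states:

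1. Twenty patients are assigned to each group (40 in total). Eligibility is settled, and assignment recorded, before any imaging.
2. No one is removed or replaced because of a later ultrasound finding, because no injection was given, or because of failure to return.
3. DASH is sought at the scheduled follow-ups from every assigned patient, injected or not, and each patient is analysed in the assigned group.
4. Uninjected patients and patients with missing scores are reported by group, with the reason.
5. A simple sensitivity analysis covers missing scores, for example by giving them values worse than the observed mean by a range of amounts, varied separately by group.

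This requires no one to be injected; an uninjected patient simply stays in the assigned group. It depends on the protocol also stating an allocation step, which it now lacks.

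The cost is wording, plus some effort to obtain scores from patients who do not return. Slightly fewer than 20 observed scores per group may be available. If, say, 18 were observed in each, the standard error would rise by a factor of √(20/18) = 1.05, about 5%.

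### The only planned comparison, of DASH scores, is not tied to the pain-relief hypothesis, not scheduled at any contact, and has no assessment time

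*Combined protocol and SAP*

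**What the plan says.** The Background section ends with the hypothesis: "We hypothesize that the US-guided injections will result in greater pain relief for patients than blind attempts". The minimal-risk paragraph of Study Design repeats the expectation of better pain relief. The summary paragraph of the same section puts the aim more broadly, as effectiveness, without defining it.

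Study Design describes four contacts. The first is a standard evaluation "which includes palpation of the first extensor compartment and application of the Finkelstein test". At 6-8 weeks and 12-16 weeks patients return and "will undergo another physical exam to determine pain relief". The fourth is remote: "A phone call follow-up will also be placed one year after the injection in order to determine long-term effectiveness". No pain scale, response definition or questionnaire is named at any of them.

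The whole of Data Analysis is one sentence: "The mean DASH scores from the control group (blind injection) and the treatment group (US-guided injection) will be compared with a t-test". This is the only mention of DASH. On timing, the plan says: "Once 20 study subjects in each group (40 total) have been enrolled and completed treatment, the data will undergo statistical analysis". On use, it says: "The results of the study will be used to validate current injection protocols or support the incorporation of ultrasonography to treat the disease".

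**The concern.** The plan schedules one kind of assessment and analyses another. The scheduled pain-relief examination has no planned between-group comparison. The planned comparison uses a score that no contact is told to collect. No sentence explains why a DASH difference would bear on the pain-relief hypothesis or on effectiveness.

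Two things are at stake. The first is data: a site that followed the visit descriptions exactly would have no DASH scores to test, and a score not taken at a visit cannot be recovered later. The second is interpretation: the result is meant to decide between keeping current practice and adopting ultrasound, and a reader cannot tell from this document which follow-up contact, or which form of the score, decides it.

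**Working it through.** **Step 1: set the contacts beside the analysis.**

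| Contact | What the plan records there | DASH named? | Between-group comparison planned? |
|---|---|---|---|
| Initial evaluation | Palpation, Finkelstein test | No | No |
| 6-8 weeks | Physical exam for pain relief | No | No |
| 12-16 weeks | Physical exam for pain relief | No | No |
| One-year call | Long-term effectiveness, no instrument | No | No |
| No contact given | DASH | n/a | t-test on means |

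DASH is scheduled at 0 of 4 contacts. The initial evaluation cannot supply a post-injection comparison, so the candidates are the 3 follow-up contacts, of which 0 are named. The score could also be raw or a change from before injection, which gives 3 × 2 = 6 readings of the sentence. A change score would need a pre-injection DASH, and none is scheduled.

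**Step 2: does the analysis trigger settle the time?** Treatment is a single injection, so completing treatment could mean the injection itself or the full study course. Neither meaning picks one of the three follow-up contacts.

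**Step 3: the plan's own figure.** The only number is 20 per group (20 × 2 = 40). It comes without alpha, power, effect size or SD, so it cannot be reproduced, and it gives no clue to the intended outcome or time.

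**Step 4: illustration of an open choice of contact.** From the document: 20 per group and the number of follow-up contacts. Assumed: two-sided alpha 0.05, normal scores, no true difference, and equal correlation r between contacts.

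At contact k, T_k = (difference in means) / (pooled SD × √(1/20 + 1/20)) on 20 + 20 − 2 = 38 degrees of freedom. The quantity sought is the probability that at least one T_k is significant. Simulation with 200,000 trials per setting gives:

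| r | Two clinic visits: either direction / favouring ultrasound | Three contacts: either direction / favouring ultrasound |
|---|---|---|
| 0.3 | 9.5% / 4.7% | 13.7% / 6.9% |
| 0.5 | 9.0% / 4.5% | 12.5% / 6.2% |
| 0.7 | 8.5% / 4.2% | 11.1% / 5.5% |
| 0.8 | 7.9% / 3.9% | 10.0% / 5.0% |

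One pre-named test gives about 5% / 2.5%. As a check, independent tests would give 1 − 0.95² = 9.75% and 1 − 0.95³ = 14.3%. The simulated values lie below these, as positive correlation requires.

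**Step 5: what baseline adjustment would add.** The document gives no effect size or SD, so a true difference of 0.8 SD is assumed; here r is the correlation between the pre-injection score and the score at the primary visit. Adjustment shrinks the residual SD by √(1 − r²), so the effective standardised difference is 0.8/√(1 − r²):
- r = 0.3: 0.8/0.954 = 0.84
- r = 0.5: 0.8/0.866 = 0.92
- r = 0.7: 0.8/0.714 = 1.12

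Simulated power (40,000 trials) is 0.69-0.70 for the t-test, against 0.73, 0.80 and 0.93 for adjusted regression. The false-positive rate is 0.049-0.052 for both.

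**The case against.** The strongest reply is that the analysis may well suit the aim. The summary paragraph speaks of effectiveness, which is wider than pain relief and which a score other than pain could serve. A reader might infer that a DASH analysis cannot answer the hypothesis. The document does not support that: it never says what DASH measures, so whether it captures pain cannot be judged here. What is shown is an unstated link, not a proven mismatch.

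A reader might also infer that the tested variable is open, pain relief or DASH. It is not. Data Analysis names one variable and one test. What is open is the contact, the form of the score, and why this variable stands for the hypothesised benefit.

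Nor does the document propose testing several contacts and reporting the best. The error rates describe what the wording leaves possible, under assumptions the plan does not give. They do not measure the gap between pain relief and DASH, and the point does not depend on them.

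Finally, regression is an improvement rather than the correction of an error. At r = 0.3 it lifts power only from about 0.70 to 0.73.

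These replies narrow the point but leave its core. No contact schedules DASH, no time is assigned to it, and the scheduled pain-relief assessment is never compared.

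**Conclusion.** The point holds on the text alone and needs correction. The single planned test has no scheduled data and no time point, and it is not tied to the hypothesis of pain relief or to the aim of effectiveness. The assessment that is scheduled has no planned test. No redaction or removed page appears to account for this. Sites may collect DASH in practice, but the document does not tell them to.

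If the contact were chosen freely, the chance of at least one false-positive difference would be about 8-10% for the two clinic visits or 10-14% with the one-year call, against 5% for one pre-named test. For a difference favouring ultrasound it would be 3.9-4.7% or 5.0-6.9%, against 2.5%. These sizes rest on the assumptions in the working; the textual finding does not.

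**What to change.** 1. Match outcome and hypothesis. Either state that DASH is the primary measure of the hypothesised benefit and restate the hypothesis accordingly, or make a patient-rated pain score primary and DASH secondary.
2. Collect every instrument that will be analysed before injection and at both existing clinic visits. If pain is primary and DASH secondary, that means both. Include the one-year call only for an instrument that can be given by telephone.
3. Name one existing clinic visit as the primary time point. The document gives no reason to prefer either, so the choice is the sponsor's. The other contacts become secondary.
4. Replace the analysis sentence with a between-group comparison of the primary score at that visit. State the test and the form of the score. A t-test there removes the ambiguity; linear regression adjusted for the pre-injection score is recommended for precision.
5. Start the analysis once the primary visit is done, or its window has closed, for all 40 patients.

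The cost is some protocol wording, one or two questionnaires at contacts that already exist (two if pain is primary and DASH secondary), the patient and staff time these take, and an analysis that waits for the primary visit. The document gives neither the length of DASH nor a telephone version, so the sponsor should check both.

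### The single planned analysis, an unadjusted t-test of mean DASH, names no visit, score type or pre-injection DASH; ANCOVA at one named visit would cost little and could improve precision if baseline and follow-up DASH correlate

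*Combined protocol and SAP*

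**What the plan says.** The analysis plan is the single sentence under Data Analysis. "The mean DASH scores from the control group (blind injection) and the treatment group (US-guided injection) will be compared with a t-test", and the purpose given is "to discern any significant statistical difference". DASH is mentioned at no other point in the document.

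Under Study Design, the evaluation before injection is described this way: "Patients will contact the PI for a standard clinical evaluation, which includes palpation of the first extensor compartment and application of the Finkelstein test". Follow-up reads: "The patient will return for follow-up appointments at 6-8 weeks and 12-16 weeks and will undergo another physical exam to determine pain relief". A telephone contact at one year is also scheduled. DASH is not tied to any of these contacts.

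On allocation, Study Design says only: "The PI will then administer either a blind or US-guided injection". On size it says: "Once 20 study subjects in each group (40 total) have been enrolled and completed treatment, the data will undergo statistical analysis". No significance level, power, target difference, standard deviation or covariate is given.

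**The concern.** Three things are left open in a trial of 40 patients.

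- **Unused information.** A t-test on follow-up scores ignores how disabled each patient was before injection. A t-test on change scores uses that information inefficiently when the correlation between the two measurements is low.
- **An open comparison.** Two in-person visits and two ways of scoring give four t-tests that all fit the sentence. If the choice is made after the data are seen, the nominal 5% no longer holds.
- **An unseen starting gap.** The allocation method is not described, so the documents do not settle whether a starting difference would be chance only. Without a pre-injection DASH, no later analysis can look for one.

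At stake are the width of the confidence interval and the credibility of a single nominal p-value.

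**Working it through.** **The plan's own figure.** The sample size of 20 per group comes without inputs, so it cannot be reproduced and is not called wrong. Solved backwards with the noncentral t (two-sided 5%, 38 df), 20 per group detects 0.91 SD with 80% power.

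**Inputs.** From the documents: 20 per group, t-test, two in-person visits. Assumed, because the documents give none: two-sided 5%; follow-up SD 20 points (range 15-25); correlation rho between pre-injection and follow-up DASH of 0.2, 0.3, 0.5 and 0.7; equal SD before and after injection, which matters only where change scores are compared.

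**Precision under random allocation.** Standard errors:

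- Follow-up t-test: SD × √(2/20) = 20 × 0.3162 = 6.32, 38 df.
- ANCOVA: SD × √[(2/20)(1 − rho²)(1 + 1/36)], 37 df. The last factor is the cost of estimating the slope, with 36 = 40 − 4. At rho 0.5: 20 × √(0.1 × 0.75 × 1.028) = 5.55.
- Change-score t-test: SD × √[(2/20) × 2(1 − rho)], 38 df.

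| rho | Detectable at 80% power: follow-up t-test | change t-test | ANCOVA | ANCOVA / follow-up | Power for 15 points: follow-up t-test | ANCOVA |
|---|---|---|---|---|---|---|
| 0.2 | 18.2 | 23.0 | 18.1 | 0.994 | 64% | 64% |
| 0.3 | 18.2 | 21.5 | 17.6 | 0.968 | 64% | 67% |
| 0.5 | 18.2 | 18.2 | 16.0 | 0.879 | 64% | 75% |
| 0.7 | 18.2 | 14.1 | 13.2 | 0.725 | 64% | 89% |

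The ratio of ANCOVA to the follow-up t-test does not depend on the SD. The follow-up t-test detects 13.6 points at SD 15 and 22.7 at SD 25; ANCOVA at rho 0.5 detects 12.0 and 20.0. Break-even is where 1.015 × √(1 − rho²) = 1, at rho about 0.17. At rho 0 ANCOVA detects 18.4 points instead of 18.2, a loss of about 1.5%.

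The change-score column depends on equal SDs. With SD 20 before and 10 after at rho 0.5, the change variance is 400 + 100 − 2 × 0.5 × 20 × 10 = 300. The change test then detects 15.7 points against 9.1 for the follow-up t-test.

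**Choosing the comparison afterwards.** Simulated under random allocation with no effect, rho 0.2-0.7 and an assumed between-visit correlation of 0.5-0.9:

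- any of four t-tests (two visits, follow-up or change): about 12-17% false positives;
- two visits, follow-up scores only: about 7-9%;
- one visit, follow-up or change: about 9%.

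This supposes that DASH is collected at both visits, which the documents do not say. It leaves out the one-year call.

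**If allocation is not random.** Suppose no treatment effect, SD 20 and a systematic 10-point difference. False-positive rates at nominal 5%, for rho 0.2, 0.3, 0.5 and 0.7 in turn:

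| Source of the difference | Follow-up t-test | Change t-test | ANCOVA |
|---|---|---|---|
| Pre-injection DASH gap that regresses to the mean (follow-up gap rho × 10) | 6, 7, 12, 19% | 16, 15, 12, 9% | about 5% |
| Pre-injection DASH gap that persists in full | 34% | about 5% | 23, 19, 14, 9.5% |
| Unmeasured factor shifting only follow-up DASH | 34% | not tabulated; full 10-point bias | 34, 36, 42, 57% |

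In the second row ANCOVA leaves a bias of (1 − rho) × 10 = 8, 7, 5 and 3 points. In the third it keeps all 10 points. Because its standard error is smaller, it then rejects falsely as often as the follow-up t-test or more often.

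**The case against.** The strongest reply is that the t-test is valid under random allocation: it keeps its 5% error rate, and replacing it is a matter of efficiency. That stands. It is also true that the gain may be trivial. At rho 0.2 it is about half a percent (18.18 to 18.07 points), and nothing in the documents supports a value of 0.5 or more. The undefined visit and score are the plainer omission, and naming them needs no ANCOVA. These points limit the weight of the recommendation. They do not remove it, because the loss if rho is zero is about 1.5%.

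Four stronger readings are tempting, and the documents support none of them.

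- *The trial is not randomised.* The method is not stated; silence does not settle it either way.
- *No DASH is taken before injection.* The described evaluation ("which includes palpation of the first extensor compartment and application of the Finkelstein test") is worded as inclusive, so an unlisted questionnaire is possible. What can be said is that the plan does not provide for one.
- *ANCOVA would protect a non-random comparison.* It does so only for a DASH gap that would regress to the mean. If the gap persists, the change-score test is the unbiased one, and with unmeasured factors ANCOVA can make false positives more frequent.
- *Twenty per group is too few.* The stated hypothesis, "We hypothesize that the US-guided injections will result in greater pain relief for patients than blind attempts", gives a direction but no size, so adequacy cannot be judged.

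**Conclusion.** The point holds as an inexpensive improvement that should be made. The plan leaves the DASH visit, the score definition and any pre-injection DASH unstated, and its only analysis is unadjusted.

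Under random allocation, ANCOVA is never more than about 1.5% worse than a follow-up t-test. It is better above rho of about 0.17 and materially better only from about 0.5. Fixing one visit and one score in advance independently removes the inflation from later choice.

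The relative gains rest on the assumed rho. The figures in points rest also on the assumed SD, and those for change scores on equal SDs before and after injection. Whether allocation is random is unknown from the documents. If it is not, which row of the last table applies cannot be tested from the data, and the benefit of adjustment is conditional.

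**What to change.** 1. Record DASH before injection at the evaluation that already takes place.
2. Name one scheduled in-person visit as primary before group results are seen. The documents give no reason to prefer either visit, so the choice, for example 12-16 weeks, belongs to the investigators.
3. Replace the t-test with ANCOVA: DASH at that visit regressed on group and pre-injection DASH, reporting the adjusted mean difference with its 95% CI.
4. Pre-specify the change-score comparison at the same visit as a sensitivity analysis. If allocation is not random and the two disagree, report that the result depends on an untestable assumption about the starting gap.
5. As a separate and prior repair, state how patients are allocated. Do not present adjustment as a substitute for randomisation.

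**Cost.** One questionnaire at an existing visit, one degree of freedom, and about 1.5% of precision if the two DASH measurements turn out uncorrelated. Under non-random allocation the further costs are those in the last table: residual bias where a change score would have none, and more frequent false positives from unmeasured factors. No baseline can be recovered for patients already injected without one. For them, naming the visit and score is still worthwhile if done before group results are seen.
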